9.2. Endpoints

- Primary effectiveness endpoint: stroke/SE (a composite of ischemic stroke, hemorrhagic stroke and SE)
- Primary safety endpoing: Major bleeding (any bleeding requiring hospitalization for treatment)

- Seconary effectiveness endpoint:
 - Cardiogenic embolic stroke
 - ➢ Ischemic stroke
- Secondary safety endpoint:
 - > Intracranial hemorrhage
 - Gastrointestinal bleeding
 - Intraocular bleeding

9.3. Setting

This study uses data from the MDV database, which includes the data used for both inpatient and outpatient insurance claims by hospitals according to the Diagnosis Procedure Combination (DPC) procedure. That is, medical information will be collected in the real-world settings.

9.3.1. Inclusion criteria

Patients must meet all the following inclusion criteria to be eligible for inclusion in the study.

- 1. Diagnosed with AF anytime in the baseline period or on the index date, also have definitive diagnosis of AF anytime in the baseline period, on the index date, or post-index period.
- 2. Prescribed apixaban or warfarin on or after the day of AF diagnosis. The first observed prescription will be used to identify the patient's index date and treatment cohort
- 3. No use of the any OACs during the baseline period (the 180 days before the index date)
- 4. Age of 18 years or older on the index date.
- 5. Index date is at age 80 or older

9.3.2. Exclusion criteria

Patients meeting any of the following criteria will not be included in the study:

- 1. Having a diagnosis of valvular atrial fibrillation, post-operative atrial fibrillation, rheumatic atrial fibrillation or mechanical-valvular atrial fibrillation during the baseline and post-index period
- 2. Having a cardiac surgery procedure record during the baseline period

- 3. Having a joint replacement procedure record during the baseline period
- 4. Having a procedure of prosthetic heart valve during the baseline period
- 5. Having a diagnosis of venous thromboembolism during the baseline period
- 6. Female patients with pregnancy during the follow-up period
- 7. Patients prescribed "off-label" doses of OACs (per Japanese package insert of each OAC) or patients treated with OAC but in "off-label" or "contraindicated" manners.

| CCI | | | |
|-----|---|--|--|
| | | | |
| | I | | |
| | | | |
| | | | |
| | | | |
| | C | | |
| | I | | |
| | | | |
| | | | |
| | I | | |
| | | | |
| | | | |
| | | | |
| | | | |
| | | | |
| | | | |
| | | | |

9.5. Variables

| Items | definitions | roles |
|--------|----------------|-------------------------|
| Gender | Male or female | Patient characteristics |
| CC | | |
| | | |
| | | |
| | | |
| | | |
| | | |
| | | |
| | | |
| | CCI | |
| | | |
| | | |
| | | |
| | | |
| | | |
| | | |
| | | |
| | | |
| | | |
| | | |
| | | |
| | | |
| | | |
| | | |
| | | |
| | | |
| | | |
| | | |
| | | |
| | | |
| | | |
| | | |
| | | |
| | | |
| | | |
| | | |
| | | |
| | | |
| | | |
| | | |
| | | |
| | | |

PFIZER CONFIDENTIAL

Page 17 of 23

| | CCI | |
|--|--|-------------------------|
| | | |
| | | |
| | | |
| | | |
| | | |
| | | |
| | | |
| Medications | | |
| The number of chronically prescribed medicine | | Patient characteristics |
| Treated with antiplatelet drug in baseline | Defined using prespecified drug-specific codes: Yes or No | Patient characteristics |
| Treated with NSAIDs in baseline | Defined using prespecified drug-specific codes: Yes or No | Patient characteristics |
| Treated with gastric secretion inhibitor in baseline | Defined using prespecified drug-specific codes: Yes or No | Patient characteristics |
| Treated with statin-based drug in baseline | Defined using prespecified drug-specific codes: Yes or No | Patient characteristics |
| Treated with anti-hypertensives in baseline | Defined using prespecified drug-specific codes: Yes or No | Patient characteristics |
| Treated with anti-arrhythmics in baseline | Defined using prespecified drug-specific codes: Yes or No | Patient characteristics |
| Treated with beta-blockers in baseline | Defined using prespecified drug-specific codes: Yes or No | Patient characteristics |
| Procedures | | |
| Cardioversion | Defined using prespecified medical procedure codes: Yes or No | Patient characteristics |
| Cardiac ablation | Defined using prespecified medical | Patient characteristics |

| procedure codes: Yes or No | |
|-------------------------------|--|
| | |

9.6. Data sources

The analysis will be based on administrative claims data provided from MDV Co. Ltd., a longitudinal database based on health insurance claims and medical records obtained from the hospitals in which the DPC payment system for utilization of both inpatient and outpatient hospital claims (percentage of inpatients is about 45%). The database provides claims data from 450 hospitals (as of Sep.2021) using the DPC system for medical service claims (21% of general hospitals but 55% of general beds in Japan is under the DPC system) including approximately 38 million patient data.

9.7. Study size

All eligible patients will be used for the analysis. The number of patients to be used for the analysis was estimated in the preliminary feasibility check and we have confirmed that the statistical power may be sufficient to the analysis.

Roughly estimated number of patients are as follows,

- Male with NVAF: \geq 80: 34,157
- Female with NVAF: \geq 80: 33,163

The number of patients who are newly diagnosed with NVAF in 80-89 or \ge 90 are not known.

The dealied results of estimation of power calculation will be described in the Statistical Analysis Plan (SAP)

9.8. Data management

Data will be securely provided by MDV Co. Ltd. All data have been structured and no development of new database and human review are not required. Provided data will be able to be used directly for the analysis.

9.9. Data analysis

Baseline patient demographic information will be compared among cohorts to be compared by appropriate tests (e.g., t-test, Mann Whitney-U test, chi-square test) based on the distribution of the measures.

Detailed methodology for summary and statistical analyses of data collected in this study will be documented in a statistical analysis plan (SAP), which will be dated, filed, and maintained by

the sponsor. The SAP may modify the plans outlined in the protocol; any major modifications of primary endpoint definitions or their analyses would be reflected in a protocol amendment.

9.10. Quality control

This study is a retrospective analysis using quality controlled structured data in a pre-existing database, and primary data collection will not be conducted. As for the data provided, quality of the data is guaranteed by MDV Co. Ltd., which has professional teams specialized in the maintenance and improvement of data quality. All these processes are consistently managed inhouse. All of operations for data management in MDV Co. Ltd. are conducted in accordance with standard operational procedures of MDV Co. Ltd.

Data analysis will be conducted by Macromill Carenet, Inc. (Tokyo, Japan). The final results will be quality checked internally by Macromill Carenet according to their internal procedures. For quality assurance of analysis, they will conduct code review of all modules of program, descriptive statistics review of all variables and patients row data examination of all output results in a test phase.

9.11. Limitations of the research methods

 The data we will use are obtained from a claims database containing information provided by hospitals applying the flat-fee payment system, which are mostly large hospitals responsible for acute care. Therefore, a significant proportion of the patients included in the present analysis are likely in poorer health than the average population requiring hospitalization, possibly having more comorbidities and higher risk of stroke/SE and bleeding.

9.12. Other aspects

There is slight duplicated analyses between and the current study and previously approved on-going study (named CER4 which will be investigated safety and effectiveness of apixaban compared to warfarin in bleeding-prone patients with NVAF)

Page 20 of 23

- CER-4 is a study focused on the risk of bleeding in the bleeding-prone (with at least one risk factor for bleeding) population taking anticoagulants. On the other hand, the current study is to investigate the risk of developing Stroke / SE and bleeding in the very elderly people receiving anticoagulant therapy. Like this, study populations to be examined are at least in part similar but basically different.
- Different, important unmet medical needs in Japan underlie these two studies. Anticoagulant therapy for patients at higher risk of bleeding and for very elderly patients are still critical unmet medical needs in Japan and these topics have been often discussed at the scientific meetings such as Japanese Circulation Society.
- A part of analysis, safety and effectiveness in very elderly patients, is suplicatedly conducted in the two study because higher age is often considered as a risk of bleeding.

In contrast, in the current very elderly patients study, patients' age is the main factor, and the effectiveness and safety of apixaban in the super-elderly will be investigated as the primary analysis.

• Therefore, two studies are quite different in the purposes, underlying unmet medical needs to be met, populations to be investigated.

10. PROTECTION OF HUMAN SUBJECTS

10.1. Patient information

This study without human review of unstructured data involves data that exist in anonymized structured format and contain no patient personal information.

10.2. Patient consent

As this study involves anonymized structured data, which according to applicable legal requirements do not contain data subject to privacy laws, obtaining informed consent from patients by Pfizer is not required.

10.3. Patient withdrawal

Not applicable

10.4. Institutional review board (IRB)/Independent ethics committee (IEC)

According to the Japanese regulations, this type of database study does not always need approval of IRB or IEC. This study is an actual survey and epidemiological study and will not submit protocol synopsis to IRB of Research Institute of Healthcare Data Science for protocol review and approval.

10.5. Ethical conduct of the study

The study will be conducted in accordance with legal and regulatory requirements, as well as with scientific purpose, value and rigor and follow generally accepted research practices described in *CT24-WI-GL02-RF04* and references to any additional relevant guidance.

11. MANAGEMENT AND REPORTING OF ADVERSE EVENTS/ADVERSE REACTIONS

This study involves data that exist as structured data by the time of study start. In these data sources, individual patient data are not retrieved or validated, and it is not possible to link (i.e., identify a potential association between) a particular product and medical event for any individual. Thus, the minimum criteria for reporting an adverse event (AE) (i.e., identifiable patient, identifiable reporter, a suspect product, and event) cannot be met.

12. PLANS FOR DISSEMINATING AND COMMUNICATING STUDY RESULTS

In the event of any prohibition or restriction imposed (e.g., clinical hold) by an applicable competent authority in any area of the world, or if the investigator is aware of any new information which might influence the evaluation of the benefits and risks of a Pfizer product, Pfizer should be informed immediately.

If not, a part or all results of the study will be published in one of the peer-reviewed medical scientific journals. No design paper, progress reports and interim reports will be published elsewhere.

13. REFERENCES 14. LIST OF TABLES 15. LIST OF FIGURES

PFIZER CONFIDENTIAL

Page 22 of 23

16. ANNEX 1. LIST OF STAND ALONE DOCUMENTS None

17. ANNEX 2. ENCEPP CHECKLIST FOR STUDY PROTOCOLS

Not applicable

18. ANNEX 3. ADDITIONAL INFORMATION

Not applicable

PFIZER CONFIDENTIAL

Page 23 of 23

1. AMENDMENTS FROM PREVIOUS VERSION(S)

From version 1.0 to version 1.1, no substantial changes have been made and only asministrative changes including correction of typos as follows; 1) in CCI

2) in 7.2.4 Summary of analysis, "time course of proportion of stroke-free" was changed to "time course of proportion of stroke/SE-free". Both changes are considered to be just administrative ones and little impact on the results would be expected.

From version 1.1 to version 2.0, two major changes have been made. Firstly, patient registration period descried in the section 2.1.1 was changed from "2008 to 2021" to "February 26, 2013 to December 31, 2021" to consider the launch date of apixaban in Japan. This change will make concurrent active control (i.e., warfarin cohort) for apixaban cohort. Secondly, calculation of propensity score was modified in the section "7.1.2.1" to adjust effect of time on treament selection (i.e., warfarin or apixaban). Propensity scores will be calculated by calendar year of index date.

2. INTRODUCTION

The number of patients with atrial fibrillation (AF) has been in the elderly patients has been increasing worldwide[1]. Especially, Japan is a very elderly society compared to other countries in Europe and the United States, and there are many very elderly patients with NVAF who are treated with any of anticoagulant and there are considerable number of patients who are newly diagnosed with NVAF even in their 80's and 90's. In the previous real-world database study conducted in Japan (CER3 study), the mean age of patients with non-valvular AF (NVAF) were 75-78 years old[2]. Most of these very elderly people have many complications, including severe ones, and take many medications chronically. In addition, many elderly patients have low body weight, sarcopenia, low ADL, frailty or frail-like characteristics, or high risk of falls. There has been much debate and inconclusive evidence on the value of anticoagulation for these very elderly patients with NVAF[1, 3, 4,]. ARISTOTLE study has shown that apixaban is superior or equivalent to warfarin in various populations including populations at higher risk. However, there are few studies in the real-world settings regarding very elderly patients who are at higher risk.

Research question and objectives :

PFIZER CONFIDENTIAL

The ARISTOTLE study and various real-world evidence (RWE) have shown that apixaban is superior or equivalent to warfarin in safety and effectiveness profile. Subgroup analyses of the ARISTOTLE study suggested that superiority over warfarin could be consistent in most populations including high risk populations. Study hypothesis and clinical questions in this study is apixaban is superior to warfarin in both safety and effectiveness even in the very elderly patients with NVAF in the real-world settings.

The clinical question of this study is that apixaban has a superior effectiveness and safety profile compared to warfarin, even in very elderly patients who are at particularly high risk, such as those with **CCL**, frail or frail patients, those with significant comorbidities, those with polypharmacy, and those at high risk of falls.

The objective of this study is to investigate safety and effectiveness of apixaban compared to warfarin in very elderly patients with NVAF.

2.1. STUDY DESIGN

This is a retrospective non-intervention observational study to evaluate the difference in safety and effectiveness between apixaban and warfarin using a database provided by Medical Data Vision Co. Ltd. (MDV Co. Ltd.). Eligible patients will be extracted from the database and allocated to the pre-defined cohorts based on the actual age, age of NVAF diagnosis and types of anticoagulant therapy.

Based on the age category and anticoagulants on the index date (a date when patients initiated an anticoagulant for prevention of stroke/SE), eligible patients will be allocated to some cohorts. Patient characteristics will be balanced by an Inverse probability of treatment weighting (IPTW) method, and risk of stroke/SE (primary effectiveness endpoint) and major bleeding (primary safety endpoint) will be compared. Hazard ratios and 95% confident intervals will be calculated by using a Cox proportional hazard method with a robust sandwich variance estimator to account for induced correlations among weighted patients.

PFIZER CONFIDENTIAL

Page 5 of 51

2.1.1. Study population

Patients registered in the MDV database from February 26, 2013 to December 31, 2021 will be used. First, patients with a NVAF diagnosis and received apixaban or warfarin as an anticoagulant after the NVAF diagnosis will be identified and then among them only patients who are 80 or older when they initiated these medications.

Based on the first anticoagulant prescribed, eligible patients will be allocated to one of two cohorts, an apixaban or warfarin cohort. Comparison will be made between these cohorts after balancing of the patient characteristics by a IPTW with stabilized weights (s-IPTW) method.

2.1.2. Data source

Medical Data Vision database, commercially available administrative claims database from hospitals introducing DPC (Diagnosis Procedure Combination) system, which comprises administrative data pertaining to approximately 39 million individuals (as of 2021 Dec.) managed in the inpatient and outpatient settings. In this database, all patients have been de-identified and no personal information resulting the identification of individuals.

PFIZER CONFIDENTIAL

Page 6 of 51

2.1.3. Treatment/cohort labels

- 1. Apixaban cohort: patients diagnosed with non-valvular atrial fibrillation who are 80 or older when they initiated apixaban as an anticoagulant.
- 2. Warfarin cohort: patients diagnosed with non-valvular atrial fibrillation who are 80 or older when they initiated warfarin as an anticoagulant.

2.2. STUDY OBJECTIVES

The objective of this study is to investigate safety and effectiveness of apixaban compared to warfarin in very elderly patients with NVAF.

The purposes of this study are 1) to characterize the primary and secondary prevention patients, 2) incidence rates of stroke/SE or major bleeding in each cohort and 3) is to investigate for Japanese secondary prevention patients as RWE on the effectiveness and safety of apixaban compared to warfarin in patients with NVAF.

3. HYPOTHESES AND DECISION RULES

3.1. STATISTICAL HYPOTHESES

Not applicable

3.2. STATISTICAL DECISION RULES

When the effect of factors in an analysis is statistically evaluated, the alpha level of 0.05 will be referred.

4. ANALYSIS SETS/POPULATIONS

4.1. FULL ANALYSIS SET

4.1.1. Inclusion criteria

Patients must meet all the following inclusion criteria to be eligible for inclusion in the study.

1. Diagnosed with AF anytime in the baseline period or on the index date, also have definitive diagnosis of AF anytime in the baseline period, on the index date, or post-index period.

PFIZER CONFIDENTIAL

Page 7 of 51

- 2. Prescribed apixaban or warfarin on or after the day of AF diagnosis. The first observed prescription will be used to identify the patient's index date and treatment cohort
- 3. No use of the any OACs during the baseline period (the 180 days before the index date)
- 4. Age of 18 years or older on the index date.
- 5. Index date is at age 80 or older

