9. RESEARCH METHODS

9.1. Study design

This is a retrospective non-intervention observational study to evaluate the difference in safety and effectiveness between apixaban and warfarin using a database provided by Medical Data Vision Co. Ltd. (MDV Co. Ltd.). Eligible patients will be extracted from the database and allocated to the pre-defined cohorts based on the actual age, age of NVAF diagnosis and types of anticoagulant therapy.

Based on the age category and anticoagulants on the index date (a date when patients initiated an anticoagulant for prevention of stroke/SE), eligible patients will be allocated to some cohorts. Patient characteristics will be balanced by an Inverse probability of treatment weighting (IPTW) method, and risk of stroke/SE (primary effectiveness endpoint) and major bleeding (primary safety endpoint) will be compared. Hazard ratios and 95% confident intervals will be calculated by using a COX proportional hazard method.

The following definitions will be used here

• Index date: the date when warfarin or apixaban was initiated

• Baseline period: the 180 days before the index date

• Cohorts:

- > Apixaban cohorts: patients who started an anticoagulant therapy with apixaban
- > Warfarin cohorts: patients who started an anticoagulant therapy with warfarin

• Observational period:

Follow-up period starts from the next day of the index date and ends depending on following outcomes which observed first.

- 1. Major bleeding when the target outcome for the analysis is major bleeding.
- 2. Composite of (ischemic or hemorrhagic) stroke and SE when the target outcome for the analysis is the composite endpoint.
- 3. Any bleeding when the target outcome for the analysis is any bleeding.
- 4. Discontinuation of the index OAC: The index treatment will be "discontinued" if the index OAC is not prescribed within 45 days after prescription refill date (calculated from the last refill date plus days of supply) of the index OAC, even though the patient has >1 medical encounter records after more than 45 days following the prescription refill date. The supposed prescription refill date is regarded as the last day of the follow-up for discontinued patients.

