4.1.2. Exclusion criteria

Patients meeting any of the following criteria will not be included in the study:

- 1. Having a diagnosis of valvular atrial fibrillation, post-operative atrial fibrillation, rheumatic atrial fibrillation or mechanical-valvular atrial fibrillation during the baseline and post-index period
- 2. Having a cardiac surgery procedure record during the baseline period
- 3. Having a joint replacement procedure record during the baseline period
- 4. Having a procedure of prosthetic heart valve during the baseline period
- 5. Having a diagnosis of venous thromboembolism during the baseline period
- 6. Female patients with pregnancy during the follow-up period
- 7. Patients prescribed "off-label" doses of OACs (per Japanese package insert of each OAC) or patients treated with OAC but in "off-label" or "contraindicated" manners.

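### New-user status rests on an empty 180-day look-back with no check that the patient was observable then, so continuing users of either drug can enter as initiators

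*SAP*

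**What the plan says.** SAP 4.1.1 and Protocol 9.3.1 carry the same five inclusion criteria. Three of them matter here:

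- New use: "No use of the any OACs during the baseline period (the 180 days before the index date").
- Index: "The first observed prescription will be used to identify the patient's index date and treatment cohort".
- AF: "Diagnosed with AF anytime in the baseline period or on the index date", so the first AF record may coincide with the index prescription.

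Protocol 9.1 defines the look-back by time alone: "Baseline period: the 180 days before the index date". Nothing in the five inclusion or seven exclusion criteria asks for a visit, claim or other record before index. Exclusions 2 to 5 of SAP 4.1.2 rely on the same period, for example "Having a procedure of prosthetic heart valve during the baseline period".

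Protocol 9.6 describes the source as "a longitudinal database based on health insurance claims and medical records obtained from the hospitals" that use the DPC system. It gives coverage as 450 hospitals and adds that "21% of general hospitals but 55% of general beds in Japan is under the DPC system". Neither document describes linkage to care given elsewhere.

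The calendar window in SAP 2.1.1 reads: "Patients registered in the MDV database from February 26, 2013 to December 31, 2021 will be used". SAP section 1 explains that the start was moved from 2008 to match the launch of apixaban. The documents do not say whether records before February 2013 may serve as look-back.

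**The concern.** In a hospital-based source, no OAC record in 180 days can mean that the patient took no OAC, or that the patient was not seen at a database hospital. The criterion does not separate the two. A patient started on an OAC at a clinic or non-database hospital, and first seen at a database hospital while still taking it, satisfies every visible criterion and is given an index date in mid-treatment.

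Two things follow. First, the cohort mixes initiators with people who have already come through their early treatment period without stopping, so time zero differs between patients. Second, an empty look-back sets the baseline covariates to absent. In SAP 7.1.2.1 nearly all the propensity covariates, including stroke or SE, bleeding, heart failure and each drug class, are defined in baseline. Weighting cannot balance a history that was never recorded, and the standardised differences would look satisfactory regardless. Both primary hazard ratios are exposed to this.

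**Working it through.** **1. Can a patient with no prior record qualify?** Take a patient aged 80 or older whose first database record is a visit at which AF is coded and warfarin is prescribed.

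- AF on the index date: met.
- Prescription on or after the AF diagnosis: met.
- No OAC in the look-back: met, because the look-back is empty.
- Age: met.
- Exclusions 2 to 5: not triggered, for the same reason.

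The patient enters as an initiator whether warfarin began that day or years before. The same holds for apixaban.

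**2. Does anything else in the plan catch this?**

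- The discontinuation, switching and withdrawal rules (Protocol 9.1) use encounter records to judge observability, but only after index.
- Propensity scores by calendar year (SAP 7.1.2.1) adjust for time, not for unseen prior use.
- No imputation (SAP 6) does not help, since an absent code is not flagged as missing.
- E-values (SAP 7.2.3), the only sensitivity analysis shown, address unmeasured confounding, not misclassified initiation.
- Protocol 9.11 does not list this as a limitation.

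Protocol 9.4 and SAP 4.4 are blacked out and cannot be checked, but the eligibility lists are complete.

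**3. Calendar start.** 26 Feb 2013 + 180 days = 25 Aug 2013. The window to 31 Dec 2021 is 3,231 days, and 180/3,231 = 5.6%. If earlier records are not used, index dates in that first 5.6% lack a full look-back. First-time attenders are affected at any date.

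**4. The plan's own figures (SAP 4.5, Table 2).** These reproduce and are not in dispute. Two-sided Schoenfeld with alpha 0.05, power 80% and 1:1 allocation gives 113 events at a hazard ratio of 0.59 and 78 at 0.53. Then 113/0.0184 = 6,141 and 78/0.0145 = 5,379, where 0.0184 and 0.0145 are the means of the two annual rates.

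**5. Illustration.** Let p be the share of continuing users in the weighted warfarin arm, q the share in the apixaban arm, and r their hazard relative to true initiators. These are assumptions; none is in the documents. With r constant over follow-up:

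observed HR = true HR × (1 − q(1 − r)) / (1 − p(1 − r))

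| p | q | r | Multiplier | Major bleeding (0.59) | Stroke/SE (0.53) |
|---|---|---|---|---|---|
| 10% | 0 | 0.8 | 1/0.98 | 0.60 | 0.54 |
| 40% | 0 | 0.6 | 1/0.84 | 0.70 | 0.63 |
| 40% | 20% | 0.6 | 0.92/0.84 | 0.65 | 0.58 |
| 40% | 40% | 0.6 | 1 | 0.59 | 0.53 |
| 30% | 0 | 1.3 | 1/1.09 | 0.54 | 0.49 |

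The result depends on the difference in contamination between arms and on whether r is below or above 1. The formula applies r to all follow-up, so it overstates the shift if the difference in hazard fades. It leaves out the effect of misread covariates.

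**The case against.** The strongest counter-argument is that contamination need not favour one arm. A reader might infer that continuing users fall mainly in the warfarin cohort and so pull the hazard ratios towards 1. The documents do not support that. Continuing apixaban users arriving from elsewhere, and long-term warfarin users switched to apixaban at the database hospital, enter the apixaban cohort by the same route. Apixaban is also the larger group in the feasibility counts (76,260 against 62,453). What remains is narrower: at the start of the window only warfarin, of the two drugs, could be in long-term use, so imbalance is most plausible early.

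Other parts of the defence also stand:

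- **The 2013 look-back.** It is tempting to say it is truncated. Extraction was scheduled for 30 Jun 2022 and the window was narrowed from 2008–2021 only in August 2023, so earlier records may be held. The point is conditional.
- **Valves.** Exclusion 1 covers valvular, rheumatic and mechanical-valvular AF diagnosed after index as well, so the valve gap is partly closed.
- **A record at or before day −180.** It does not prove observation during the 180 days and cannot reveal OACs prescribed outside database hospitals.
- **Restricting the primary cohort.** This would drop patients whose first hospital contact is the AF presentation, and newly diagnosed patients in their 80s and 90s are central to the rationale.
- **Sample size.** The pool of 76,260 + 62,453 = 138,713 was counted before any criteria, so it does not show how many would remain after a filter.

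None of this supplies the missing observability check or a way to see its effect.

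**Conclusion.** The gap is real and appears in both documents: new use is inferred from absent records, with no condition that the patient could have been observed. It lets continuing users of either drug into the cohorts and misreads their history in the propensity score.

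How much this moves the two primary hazard ratios, and in which direction, is unknown. The ranges 0.60 to 0.70 and 0.54 to 0.63 rest on assumed values (p of 10% to 40%, r of 0.6 to 0.8, no apixaban contamination) and are not estimates. The concern is bias, not power. It does not show that the primary cohort definition must be replaced; it calls for an inexpensive addition that would measure the problem.

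**What to change.** 1. In SAP 7.2.3, add a sensitivity analysis of both primary endpoints restricted to patients with at least one database record 180 days or more before index, and preferably also an encounter within the 180 days. Re-estimate propensity scores and weights in that subset.
2. Report, by cohort and index year, the share of patients with no record before index. This shows directly whether the arms differ and whether the early years stand out.
3. State whether records before 26 Feb 2013 are available as look-back. Use all earlier extracted records, not only the last 180 days, to detect prior OAC use and prosthetic valves. If pre-window records are not used, start index dates at 25 Aug 2013.
4. Add to Protocol 9.11 the residual limitation that OACs prescribed outside database hospitals remain unseen.

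The cost is some wording in both documents, one cohort filter and one additional weighted analysis. The restricted cohort will be smaller and tilted towards patients already in care at the hospital, so it is proposed as a sensitivity analysis and not necessarily as the primary one.
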